Comparator Device	Daavlin 7 series 3 panel narrow band phototherapy home units (have 8-12 bulbs and a smaller, flat surface with door, measuring 21" wide, 74.5" tall, and 23.5"). The unit will have a dosimetery controller, a UV sensor built in that measures the intensity of the light. This unit is a class II device with a FDA 510K indication for psoriasis, vitiligo and atopic dermatitis/eczema.
Duration of administration (if applicable)	Approximately three times per week x 12 weeks

Reference therapy	Office based narrow band phototherapy (units typically have at least 24 bulbs in a surround structure)
Statistical Methodology	 The co-primary endpoints of this study will be: Physician Global Assessment (PGA) score of clear/almost clear (at week 12 or the time of phototherapy discontinuation, whichever comes first) Dermatology Life Quality Index (DLQI) score of ≤5 which corresponds to no to small impact of dermatologic disease on quality of life at week 12 Secondary outcomes include: Physician measured body surface area (BSA) x PGA Concomitant topical psoriasis treatment Patient reported time spent on phototherapy Patient reported time and cost associated with travel for phototherapy treatments Phototherapy number and dose Duration of treatment response during observation period
Safety Evaluations	The primary safety outcome is the proportion of patients reporting treatment- emergent adverse events. Treatment emergent adverse events include patient reported burns and their severity. We will also collect data on all Serious Adverse Events whether treatment related or not.
Data and Safety Monitoring Plan	The local investigators are responsible for monitoring patient safety as per standard of care. Data quality will be monitored by the study Principal Investigator and his team centrally with queries and auditing of sites as necessary.

BACKGROUND AND STUDY RATIONALE

This study will be conducted in full accordance all applicable University of Pennsylvania Research Policies and Procedures and all applicable Federal and state laws and regulations including 45 CFR 46, 21 CFR Parts 50, 54, 56, and Good Clinical Practice: Consolidated Guidelines approved by the International Conference on Harmonisation (ICH).

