3.2.3 Primary Safety Endpoints

The primary safety outcome is the proportion of patients reporting treatment-emergent adverse events. Adverse events include patient reported burns and their severity. Patients will be queried about these events immediately prior to each phototherapy treatment by the clinical staff (for patients assigned to office base phototherapy) or by the home phototherapy machine. We will also evaluate all serious adverse events regardless of their relationship to treatment. All patients will be queried about SAEs by the sites at the visit 2. Patients can spontaneously report SAEs at any point during the study.

4 Study Population and Duration of Participation

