6.3 Observational Period (Weeks 13-24)

6.3.1 Week 16, 20 & 24

- Patient reported DLQI
- Patient reported target lesion image
- Patient reported psoriasis topical treatment
- Site reported oral and biologic psoriasis medications (at week 24)

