9.1 Definitions

9.1.1 Adverse Event

An **adverse event** (AE) is any symptom, sign, illness or experience that develops or worsens in severity during the course of the study. For the purpose of this pragmatic trial, for which the intervention occurs during standard of care visits, we will only record and collect data on adverse events that are specifically related to phototherapy treatment, except for serious adverse events which will be collected regardless of relationship to phototherapy.

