9.2 Recording of Adverse Events

This pragmatic trial will be evaluating the effectiveness of two standard of care treatments, home and office-based phototherapy. All treatments will be administered and monitored by the patient's clinical care provider (dermatologist) and designated staff (typically phototherapy nurses). Recording of reported adverse events will be completed by the patient's clinical care provider(s) prior to the administration of each treatment (3 times per week) and the clinical course of each event will be followed until resolution, stabilization, or until it is determined that phototherapy is not the cause. Adverse events will be documented in the patient's medical record by the clinical care provider(s) throughout the 12 week intervention period and the subsequent 12 week observation period per local practice or medical center requirements. Only phototherapy-emergent adverse events will be abstracted from medical records and/or home phototherapy equipment and recorded for study objective purposes.

Serious adverse events will be recorded and monitored by the patient's clinical care provider(s), per standard of care practices, and will also be recorded, tracked, and reported by the study in the appropriate case report form and SAE reporting form at Visit 2. Serious adverse events that are identified at the end of the study intervention period will be followed up to determine the final outcome. Any serious adverse event that occurs after the study intervention period and is considered to be possibly related to the study intervention or study participation will be recorded and reported immediately.

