9.3 Relationship of AE to Study

For the purpose of this pragmatic trial, for which the intervention occurs during standard of care visits, we will only record and collect data on adverse events that are specifically related to phototherapy. The Site Investigator or designee will review all AEs.

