9.4.2 Investigator reporting: notifying the study sponsor

Any study-related unanticipated problem posing risk to subjects or others, and any type of serious adverse event, will be reported to the study sponsor by telephone within 24 hours of the event. Report serious adverse events by phone and email to:

[name] MD, MSCE [contact]-SKIN Email: [contact]

Within the following 48 hours, the local site investigator will document and provide further information, if available, on the serious adverse event or the unanticipated problem in the form of a written narrative report. Significant new information on ongoing serious adverse events should be provided promptly to the study sponsor. The local site investigator will keep a copy of the SAE report on file at the study site.

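### The SAE scope is stated inconsistently, and the only scheduled SAE query is at Visit 2, which covers at most about half of follow-up and less for early stoppers

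*Combined protocol and SAP*

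**What the plan says.** **Scope.** Four places cover every SAE.
- Study Summary, Safety Evaluations: "We will also collect data on all Serious Adverse Events whether treatment related or not".
- Section 3.2.3: "We will also evaluate all serious adverse events regardless of their relationship to treatment".
- Section 9.1.1 limits adverse event data to phototherapy-related events, "except for serious adverse events which will be collected regardless of relationship to phototherapy". It defines an adverse event over the whole course of the study.
- Section 9.4.2 requires that "any type of serious adverse event, will be reported to the study sponsor by telephone within 24 hours of the event", with no limit by relationship or period.

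Two places read more narrowly.
- Section 9.3: "we will only record and collect data on adverse events that are specifically related to phototherapy. The Site Investigator" or a designee then reviews all AEs. The SAE exception is not repeated. The introduction to Section 9 likewise says that unrelated AEs are not recorded for the study, without the exception.
- Section 9.2, for the later period, names for recording and immediate reporting any SAE that "occurs after the study intervention period and is considered to be possibly related to the study intervention or study participation". It does not mention unrelated SAEs in that period.

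**Timing.** Section 3.2.3 states: "All patients will be queried about SAEs by the sites at the visit 2". Sections 6.2.5 and 7.6 agree, and Section 9.2 ties the study's SAE form to the same visit. Under Section 6.2.5, Visit 2 falls at week 12 plus or minus 2 weeks, or at discontinuation of phototherapy if that is earlier. Section 3.1.2 nevertheless fixes the intervention phase at 84 days, and Section 3.1.3 adds an 84-day observation phase. Section 6.3.1 lists no SAE item at weeks 16, 20 or 24, although sites report oral and biologic psoriasis drugs at week 24. Patients may also report SAEs spontaneously at any time (Sections 3.2.3 and 7.6).

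**The concern.** A site that learns of an unrelated hospital admission at week 18 is told to record and report it by Sections 9.1.1 and 9.4.2. Section 9.3, and one reading of Section 9.2, suggest that it need not. Sites may resolve this differently.

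Separately, the date of the only active query depends on when the patient stops phototherapy, which is an event after randomization. Someone who stops early is asked about SAEs once, at that point. The text schedules no further query for the rest of the intervention phase or for the observation phase. At stake is whether the planned evaluation of all SAEs rests on comparable ascertainment across patients and, if stopping differs by arm, across arms.

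**Working it through.** **Inputs.** Intervention phase 84 days (3.1.2). Observation phase 84 days (3.1.3). Visit 2 at week 12 plus or minus 14 days, or at discontinuation if earlier (6.2.5). One scheduled SAE query, at Visit 2 (3.2.3, 6.2.5, 7.6).

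**Reproducing the plan's figure.** 84 + 84 = 168 days after the start of phototherapy, and 168 + 28 days of screening = 196. Both match Section 4.4.

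**Share of follow-up covered by the active query.** Covered share = day of Visit 2 / 168. Intervention days left after the query = 84 − day of Visit 2, or 0 if negative.

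| Visit 2 on day | Covered share | Intervention days left |
|---|---|---|
| 98 (end of window) | 98/168 = 58% | 0 |
| 84 | 84/168 = 50% | 0 |
| 70 (start of window) | 70/168 = 42% | 14 |
| 56 (stops early) | 56/168 = 33% | 28 |
| 28 (stops early) | 28/168 = 17% | 56 |
| 14 (stops early) | 14/168 = 8% | 70 |

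**When the arms would differ.** Suppose a fraction *d* of an arm stops at day *t* and the rest have Visit 2 at day 84. The average covered share is (*d·t* + (1 − *d*)·84)/168. If *t* is the same in both arms, the gap between them is (difference in *d*) × (84 − *t*)/168. It is zero when stopping rates are equal. The documents give no rates, so the following shows sensitivity only and is not a forecast. For an assumed 10% against 30% stopping, the gap is 0.20 × 28/168 = 3.3 percentage points at *t* = 56 (48.3% against 45.0%). At *t* = 28 it is 0.20 × 56/168 = 6.7 points (46.7% against 40.0%). Which arm would be lower is unknown.

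**Scope statements side by side, for an unrelated SAE.**
- *Up to day 84:* the Study Summary and Sections 3.2.3, 9.1.1 and 9.4.2 require it. The post-intervention sentence in 9.2 does not apply. Only 9.3 and the Section 9 introduction, read literally, exclude it.
- *After day 84:* 9.1.1 and 9.4.2 still require it. Section 9.2 is silent on it, and 9.3 read literally excludes it. No section of the text sets out how it would be actively sought.

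**The case against.** The strongest reply is that the texts can be reconciled. The sentence in Section 9.2 ends by calling for immediate recording and reporting, so it may be an urgency rule for late, possibly related SAEs. It does not say that unrelated late SAEs go unrecorded. Section 9.3 may simply be shorthand for 9.1.1. This stands in part: 9.2 is ambiguous rather than plainly contradictory. Section 9.3 still omits an exception that 9.1.1 makes explicit.

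A reader might infer that nothing is captured after Visit 2 unless the patient volunteers it. That goes too far. Clinicians record SAEs under standard of care, charts document adverse events through both 12-week periods (9.2), and sites must report any SAE within 24 hours (9.4.2). These routes are passive or depend on the site hearing of the event, and 9.2 abstracts only phototherapy-emergent AEs from the chart. Late capture is thus weaker, not absent.

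A reader might also infer that a relatedness judgement made with knowledge of the arm decides which SAEs count. Section 3.1.4 does blind only the data analysts. But under 9.2 such a filter could operate only after day 84, and only on the restrictive reading. A patient who stops at week 4 is still in the intervention phase until day 84.

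Two further points stand. Section 7.4 says all evaluations appear in Appendix D, and Sections 9.5.1 and 11.1 place monitoring in Appendix F. Neither appendix's content is in the text reviewed, and either could add an SAE query. Also, the primary safety outcome is treatment-emergent adverse events, with burns queried before each treatment. No SAE hypothesis is specified, and light-touch collection is a deliberate feature of a pragmatic trial.

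**Conclusion.** The point holds as a minor, inexpensive improvement. The scope wording is inconsistent between the Study Summary and Sections 3.2.3, 9.1.1 and 9.4.2 on one side and Section 9.3 on the other, with 9.2 ambiguous. In the text available, active SAE ascertainment covers about 50% of the 168 days when Visit 2 is at day 84 (42% to 58% over the window). It covers 33% or 17% when phototherapy stops at day 56 or day 28. These shares follow from the plan's own day counts and assume that Appendices D and F add no query.

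Unequal capture between arms is tempting to conclude, but the documents do not support it. Through this mechanism it would need stopping rates or timing to differ by arm, and no rates are given. With equal stopping there is no difference. Nor do the Study Summary or Section 3.2.3 promise collection through week 24. That window can be inferred only from the definition in 9.1.1 together with the 168 days of participation in 4.4. The effectiveness analyses are unaffected.

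**What to change.** 1. Reconcile Sections 9.1.1, 9.2, 9.3 and 9.4.2, and the introduction to Section 9, to one SAE scope and one collection window with stated start and end days. Apply it equally to both arms, whether or not phototherapy has stopped. Keep the Section 9.2 sentence only as an immediate-reporting rule, if that is its intent, and label it as one.
2. Unless Appendix D or F already provides this, add an SAE question at week 12 for patients whose Visit 2 came early, and at week 24 for everyone. Sites already report oral and biologic drugs at week 24 (6.3.1). Patients complete surveys every 4 weeks (3.1) and are encouraged to stay in the study regardless of adherence (6.5), so early stoppers should be reachable.
3. In the safety analysis (8.4.3), report SAEs by arm separately for the intervention and observation phases, with time at risk.

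The cost is wording changes, two extra questions at existing contacts and some added SAE paperwork. Sample size and the effectiveness analyses do not change.

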9.3 Relationship of AE to Study

For the purpose of this pragmatic trial, for which the intervention occurs during standard of care visits, we will only record and collect data on adverse events that are specifically related to phototherapy. The Site Investigator or designee will review all AEs.

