8.4.3 Safety Analysis

The primary safety outcome is the proportion of patients reporting treatment-emergent adverse events. Adverse events include patient reported burns and their severity. We hypothesize that safety of home based UVB phototherapy will not be different from office based phototherapy. We anticipate based on extensive experience, that the number of clinically significant burns (i.e., which may require the patient to seek advice from the treating physician and occur due to human error) will be rare (affecting <1% of patients) and typically can be managed at home with over the counter remedies.

As ultraviolet light does not have adverse effects beyond the skin, our stakeholders believe that safety assessments should focus on skin related events such as burns and serious adverse events. We will summarize the number, severity, and type of adverse events experienced by patients in each treatment arm. We will compute the proportion of patients experiencing adverse events by treatment arm, with 95% CI. Similar to analyses for our effectiveness outcomes, we will also fit skin type-adjusted logistic regression models and use standardization to estimate adjusted risk differences between treatment arms. In addition to pooled safety analyses, we will also compare the proportion of patients experiencing adverse events between office-based and home-based phototherapy arms within each skin type sub-group

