8.5 Subject Population(s) for Analysis

The primary analysis will be based on all subjects randomized into the study, regardless of whether they received the assigned treatment. We will also conduct an "as treated" analysis in order to evaluate those who completed the study and received at least 80% of treatments

9 Safety and Adverse Events

Designated site personnel at each site have the front-line responsibility of reviewing patient-reported response to phototherapy, identifying and documenting treatment emergent adverse events, and adjusting phototherapy dosing accordingly. The Sponsor/Study Principal Investigator is responsible for tracking these reports and relaying them, if required, to the IRBs and other investigators. For this pragmatic study, where intervention is standard of care and performed by the patient's clinician or the patient themselves (in the case of home treatment), AE's not related to phototherapy are not required to be recorded or followed by patient's clinician and will not be recorded for study purposes.

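### The primary safety outcome is labelled treatment-emergent, but non-serious events are kept only if linked to phototherapy, and arm-aware site staff identify and review them without stated criteria

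*Combined protocol and SAP*

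**What the plan says.** Section 3.2.3 sets the outcome: "The primary safety outcome is the proportion of patients reporting treatment-emergent adverse events". It includes burns and their severity. Patients are asked before each session, by clinic staff in the office arm and by the machine in the home arm. Section 8.4.3 repeats the definition and plans the comparison: "We will compute the proportion of patients experiencing adverse events by treatment arm, with 95% CI", followed by risk differences adjusted for skin type and comparisons within each skin type.

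The safety sections then narrow what enters the study data:

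- Section 9, opening paragraph: "AE's not related to phototherapy are not required to be recorded or followed by patient's clinician and will not be recorded for study purposes".
- Section 9.1.1: the same restriction, "except for serious adverse events which will be collected regardless of relationship to phototherapy".
- Section 9.2: only events termed phototherapy-emergent are abstracted, whether from the chart or from the home unit. Each event is also followed clinically, as in "the clinical course of each event will be followed until resolution, stabilization, or until it is determined that phototherapy is not the cause".
- Section 9.3: "we will only record and collect data on adverse events that are specifically related to phototherapy".

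On who handles the events, section 9 says "Designated site personnel at each site have the front-line responsibility of reviewing patient-reported response to phototherapy", and gives the same staff the task of identifying and documenting events. Section 9.3 adds "The Site Investigator or designee will review all AEs". Section 3.1.4 blinds the data analysts by coding the groups. No blinding of site staff is described.

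**The concern.** The label and the data kept follow different rules. A treatment-emergent outcome is defined by when an event starts. The retained non-serious events are defined by cause. Assigning cause takes judgement, and the staff closest to it either gave the session themselves or prescribed a unit for use at home. A reddened area could be put down to the light, to sun or to a topical product, and that call could lean differently in the two arms.

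The stakes are real. Tolerability is part of the primary objective (section 2.1). Sections 1 and 1.3 raise the possibility that burns differ by arm in skin type I/II. Section 1.1 reports that doubt about the safety of home units discourages prescribing. A selection step applied with knowledge of the arm could create a difference or hide one.

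**Working it through.** The plan gives no figure to reproduce here: it states no expected overall adverse event rate and no retention rate. The check is a reading of the text, followed by an illustration on assumed values.

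**Text, step by step**

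1. *Outcome as named:* any treatment-emergent event that a patient reports (3.2.3, 8.4.3).
2. *Outcome as collected:* non-serious events linked to phototherapy, plus all serious events (9, 9.1.1, 9.2, 9.3; also 3.2.3 for serious events).
3. *Who stands between report and record:* site personnel review responses and identify events (9), and the site investigator or designee reviews all events (9.3). Section 9.2 applies its restriction to home-unit data as well as charts, so device answers are not clearly exempt.
4. *Criteria:* none are given for relatedness, and none for which answer on the response question counts as an adverse event. Section 1.3 treats slight redness lasting under 24 hours as the desired response, so expected effect and adverse event have to be separated somewhere.
5. *Blinding:* stated for analysts only (3.1.4).

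**Illustration of size**

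Inputs:

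- True risk p, equal in both arms: assumed at 1%, 10% and 20%. For context, section 8.4.3 expects clinically significant burns in under 1% of patients, and section 1.2.3 cites mild erythema in 10% and 15% of treated children in two studies.
- Fraction of events retained: assumed at 0.90 in one arm and 0.70 in the other. Either arm could be the higher one.
- Patients per arm: 525 (1050/2, section 4.5) or 390 ((350 + 350 + 80)/2, from the stratum sizes in section 3.1).

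Formulas: false difference = p × (0.90 − 0.70). With a = 0.90p and b = 0.70p, SE = √{[a(1 − a) + b(1 − b)]/n} and z = (a − b)/SE. The chance of a nominal two-sided p < 0.05 is P(Z > 1.96 − z) + P(Z < −1.96 − z).

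Worked case, p = 20%, n = 390: a = 0.18 and b = 0.14; SE = √[(0.1476 + 0.1204)/390] = 0.0262; z = 0.04/0.0262 = 1.53; chance = 0.332.

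| True risk, both arms | Recorded | False difference | Chance of p < 0.05, 390 per arm | 525 per arm |
|---|---|---|---|---|
| 1% | 0.9% v 0.7% | 0.2 points | 0.061 | 0.065 |
| 10% | 9% v 7% | 2 points | 0.178 | 0.223 |
| 20% | 18% v 14% | 4 points | 0.332 | 0.425 |

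Without a retention difference the false difference is zero and the chance is 0.05. At 1% risk only about three events per arm would be recorded (0.009 × 390 = 3.5 and 0.007 × 390 = 2.7), so the normal approximation is rough in that row.

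Masking works the same way. A true 25.7% at home with 70% retained, and 20% in the office with 90% retained, would both be recorded as 18% (0.257 × 0.70 = 0.180; 0.20 × 0.90 = 0.180). A true difference of 5.7 points would disappear.

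**The case against.** The strongest case against runs as follows, and much of it stands.

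- *Serious events are exempt.* A reader of section 9.3 alone might infer that only related events are collected at all. Sections 3.2.3 and 9.1.1 rule that out. This stands; the point concerns non-serious events.
- *Burns may never meet a causality call.* The response question in section 7 asks about redness induced by the previous session, so it presumes the cause, and home answers are stored on the device. A reader might infer that the burn comparison is demonstrably filtered. The documents do not show this, and they do not settle whether such answers count automatically or only after site review. For burns the filter is a risk. It is not excluded, because sections 9 and 9.2 place site staff and a restriction between the answers and the recorded events.
- *The data exist.* A reader might infer that the named outcome cannot be computed. The pre-session answers are collected in both arms, so the patient-reported skin component can be. What is lost is non-serious events attributed to something else, an exclusion that the plan discloses and justifies by its pragmatic design and its focus on skin events.
- *The follow-up wording is not an inclusion rule.* The sentence in section 9.2 on determining the cause governs how long an event is followed, and section 9.3 gives nobody the relatedness decision by name. Both are correct. That site staff make the decision is an inference, though a natural one from sections 9 and 9.3.
- *The magnitudes are assumed.* This stands in full. Section 8.4.3 also sets no significance rule for safety, so the chances in the table describe how a reader might take the interval, not a planned decision.

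The response questionnaire and the data safety plan are listed in section 16 but are not in the text available here. If either contains a classification rule, section 8.4.3 should cite it.

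**Conclusion.** The mismatch is real: the outcome is named by onset and patient report, while non-serious events are kept by their link to phototherapy. Arm-aware site staff identify and review the events, with no relatedness criteria stated in the text available. The arm comparison may therefore be affected by an unblinded selection step.

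It would go too far to say that the reported difference is biased or that it will be off by a particular amount. Under equal true risk and 90% v 70% retention, the false difference runs from 0.2 points at 1% risk to 4 points at 20%. It reverses sign if the retained fractions are swapped and vanishes if they are equal. Nothing in the documents fixes the risk, the fractions or the direction. The change is worth making because it closes this route for the skin component at little cost, not because bias has been demonstrated.

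**What to change.** In sections 8.4.3 and 9.3:

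1. Derive the skin-reaction and burn component in both arms directly from the pre-session patient answers, whatever the site's attribution.
2. Pre-specify one degree and duration category that counts as an event, and apply it identically to device-recorded and staff-entered answers, so that expected brief redness is handled alike. Without such a category, counting every reaction would sweep in the intended effect.
3. Record the site's attribution as a separate variable.
4. Report the related-only proportion and clinician-reported events as sensitivity analyses.
5. Describe the remainder of the outcome as related non-serious events plus all serious events.

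The cost is protocol wording and one extra table, since the answers are already collected. Some skin reactions not caused by phototherapy will be counted in both arms.

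Two limits remain. Patients are still asked by staff in one arm and by a machine in the other, and this change does not remove that difference. Section 5.6 also accepts that some home units will not be returned, so the plan should say how a home patient without a device record is counted.
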